9.1.6. Deviations in physical examination

Blood pressure, heart rate assessment.

9.1.7. Deviations in the results of other additional tests

Not applicable.

9.2. Recording and monitoring the further course-related of adverse events

During each visit patients well-being will be recorded.

Each related adverse events will be recorded on the relevant pages of the Observation Form. The related adverse event should be recorded, including drug reactions, disease beginning during the observation or exacerbation of pre-existing disease.

Previously reported related adverse event which is recognized as "ongoing" shall be checked during each subsequent assessment.

For each recorded related adverse events Investigator must seek to obtain adequate information to determine the course of the related adverse events and to assess whether it meets the criteria for the classification of a related serious adverse event, that requires immediate (within 24 hours) notification to the Study Organizer. The Investigator must assess the causal relationship between the study drug administration and the occurrence of related adverse events and record the results of the evaluation in the Observation Form. Discontinuation of treatment with the study drug is necessary if the related event or its consequences are still present the next day after the related adverse event was recorded. Further monitoring is needed to down grade the event or its consequences, or to stabilize them at a level acceptable by investigator or a designated representative from the Office Study Organizer.

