THE ASSESSMENT OF SAFETY PROFILE AND TOLERANCE OF ZOLEDRONIC ACID ACTAVIS® FORMULATION IN POLISH PATIENTS POPULATION

PROTOCOL OF NON-INTERVENTIONAL, POST-MARKETING STUDY

STUDY NUMBER: EPH/ACID/2014/023/001

The investigator-coordinator: [name], MD, PhD

Contact in case of adverse events:

[contact] [name] [contact] [contact]

Office of Study Organizer : EUROPHARMA M. Rachtan Sp.z oo

[name] [contact] [contact]

LEGAL NOTICE:

This Protocol does not in any way constitute a basis for a decision on any diagnostic or therapeutic methods with respect to any participant of the study. In accordance with Art. 36u paragraph. 2 of the Act of 6 September 2001 - Pharmaceutical Law (Journal of Laws 2001 No. 126, item. 1381), Study Protocol requires approval by the President of the Office for Registration of Medicinal Products, Medical Devices and Biocides and obtain consent for its conducting

SIGNATURES ON A PROTOCOL

Investigator Signature:

I confirm that I have read the protocol of non-interventional, post-marketing study entitled:

THE ASSESSMENT OF SAFETY PROFILE AND TOLERANCE OF ZOLEDRONIC ACID ACTAVIS® FORMULATION IN POLISH PATIENTS POPULATION

I am aware of investigator responsibilities imposed on me resulting from binding regulations and Study Protocol. I agree to conduct of this study in accordance with these guidelines.

| NAME AND LAST NAME: | | SIGNATURE: | |
|--------------------------------|--------------|------------|--|
| POSITION: | Investigator | | |
| ADDRESS THE MEDICAL CENTER: | | DATE: | |
| | | | |

PROJECT TITLE THE ASSESSMENT OF SAFETY PROFILE AND TOLERANCE OF ZOLEDRONIC ACID : ACTAVIS® FORMULATION IN POLISH PATIENTS POPULATION

| THE AIMS | The main | aim of | the study: |
|----------|----------|--------|------------|
|----------|----------|--------|------------|

The assessment of safety profile of ZOLEDRONIC ACID ACTAVIS formulation in patients with advanced malignancies involving bone.

Additional aim of the study:

The assessment of the treatment tolerance.

| PHASE OF THE STUDY: | Non -interventional, post-marketing study, hereinafter referred to as 'Observing Program' |
|--|--|

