To prepare an infusion solution concerning 4 mg Zoledronic acid Actavis further dilute the Zoledronic acid Actavis concentrate (5,0 ml) with 100 ml calcium-free or other divalent cation-free infusion solution. If a lower dose of Zoledronic acid Actavis is required, first withdraw the appropriate volume as indicated below and then dilute it further with 100 ml of infusion solution. To avoid potential incompatibilities, the infusion solution used for dilution must be either 0.9% w/v sodium chloride or 5% w/v glucose solution.

Introduction for preparing reduced dose of Zoledronic acid Actavis:

Withdraw the appropriate volume of the liquid concentrate, as follows:

- » 4.4 ml for 3.5 mg dose
- » 4.1 ml for 3.3 mg dose
- » 3.8 ml for 3.0 mg dose

The solution containing zoledronic acid is given as a single 15-minute intravenous infusion in a separate infusion line. The hydration status of patients must be assessed prior to and following administration of Zoledronic acid Actavis to ensure that they are adequately hydrated.

Do not mix Zoledronic acid Actavis concentrate with calcium-containing or other divalent cation containing solution such as lactated Ringer's solution. Since no data are available on the compatibility of Zoledronic acid Actavis with other intravenously administered substances. Zoledronic acid Actavis must not be mixed with other medications/substances and should always be given through a separate infusion line.

For single use only. Any unused solution should be discarded. Only clear solution free from particles and discolouration should be used. Aseptic techniques must be followed during the preparation of the infusion.

Healthcare professionals are advised not to dispose of unused Zoledronic acid Actavis via the domestic sewage system. Any unused medicinal product or waste material should be disposed of in accordance with local requirements.

The recommended dose in the prevention of skeletal related events in patients with advanced malignancies involving bone is 4 mg zoledronic acid every 3 to 4 weeks. Patients should also be administered on oral calcium supplement of 500 mg and 400 IU vitamin D daily. The decision to treat patients with bone metastases for the prevention of skeletal related events should consider that the onset of treatment effect is 2-3 months.

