When initiating treatment with Zoledronic acid Actavis in patients with multiple myeloma or metastatic bone lesion from solid tumors, serum creatinine and creatinine clearance (CLcr) should be determined. CLcr is calculated from serum creatinine using Cockcroft-Gault formula. Zoledronic acid Actavis is not recommended from patients presenting with severe renal impairment prior to initiation of therapy, which is defined for this population as CLcr < 30 ml/min.

In patients with bone metastases presenting with mild to moderate renal impairment prior to initiation of therapy, which is defined for this population as CLcr 30-60 ml/min, the following Zoledronic acid Actavis dose is recommended:

- » baseline creatinine clearance > 60 ml/min Zoledronic acid Actavis recommended dose is 4.0 mg zoledronic acid,
- » baseline creatinine clearance 50-60 ml/min Zoledronic acid Actavis recommended dose is 3.5 mg zoledronic acid,
- » baseline creatinine clearance 40-49 ml/min Zoledronic acid Actavis recommended dose is 3.3 mg zoledronic acid,
- baseline creatinine clearance 30-39 ml/min Zoledronic acid Actavis recommended dose is 3.0 mg zoledronic acid.

Following initiation of therapy, serum creatinine should be measured prior to each dose of Zoledronic acid Actavis and treatment should be withheld if renal function has deteriorated. In the clinical trials, renal deterioration was defined as follows:

- » For patients with normal baseline serum creatinine (<1.4 mg/dl or <124 micromol/l), an increase of 0.5 mg/dl or 44 micromol/l;
- » For patients with abnormal baseline creatinine (>1.4 mg/dl or >124 micromol/l), an increase of 1.0 mg/dl or 88 micromol/l.

In the clinical studies, zoledronic acid treatment was resumed only when the creatinine level returned to within 10% of the baseline value. Zoledronic acid Actavis treatment should be resumed at the same dose as that given prior to treatment interruption.

Patients must be assessed prior to administration of Zoledronic acid Actavis to ensure that they are adequately hydrated. Overhydration should be avoided in patients at risk of cardiac failure.

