3. STUDY DESIGN

3.1. Basic information

This is a non-interventional, post-marketing study. This study collects data on the occurrence of any adverse events and tolerability of **ZOLEDRONIC ACID ACTAVIS** formulation during treatment of patients **WITH ADVANCED MALI-GNANCY INVOLVING BONE**. Treatment with this preparation should follow the instructions specified in the Summary of Product Characteristics. Patient inclusion of the study is independent of the previous decision regarding the treatment of the patient with **ZOLEDRONIC ACID ACTAVIS** formulation.

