6.2 Visits to a specialist clinic under the study

6.2.1 Screening visit (day 0, visit 1)

All patients will use ZOLEDRONIC ACID ACTAVIS in accordance with the decision of the treating physician and in accordance with the conditions contained in the Summary of Product Characteristics. In the Observation Form the following information will be recorded:

- » patient number
- » patient initials
- demographic data
- » data on primary disease
- » data on treatment with ZOLEDRONIC ACID ACTAVIS
- » concomitant diseases on the basis of medical history
- » data on pharmacotherapy of concomitant diseases
- » determination of the inclusion and exclusion criteria
- » data on tolerance of treatment with ZOLEDRONIC ACID ACTAVIS in opinion of the patient
- » data on adverse events related to treatment with **ZOLEDRONIC ACID ACTAVIS**.

6.2.2 Control visit 2 at least two months from the date of 1st visit according to the date of the planned visit arising from clinical needs of the patient

Patients will be reported on visits to the center for a set period of time. These visits will be conducted in accordance with the plan as part of routine follow-up of the Patient and time set according to the individual clinical needs. During these visits, the Investigators will collect and recorded in the Observation Form (CRF) information on the current course of the primary disease, its current treatment, adverse events related to treatment with ZOLEDRONIC ACID ACTAVIS, potential changes of pharmacotherapy used in primary disease and concomitant disease treatment and assessment of tolerance treatment with ZOLEDRONIC ACID ACTAVIS in the opinion of the patient.

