8. STUDY DRUG

8.1 Administration of the drug

The drugs will be used based on a recommendation by the treating doctor, after realizing the prescription at the public pharmacy.

Study drug

ZOLEDRONIC ACID ACTAVIS is a formulation containing the active substance having the chemical name zoledronic acid (as monohydrate)

Pharmaceutical form: sterile, clear and colourless concentrate for infusion.

Potency: one ml concentrate contains 0.8 mg zoledronic acid (as monohydrate)

List of experiences: mannitol, sodium citrate, water for injections

Name and address of the manufacturer responsible for batch release:

Actavis Group PTC ehf. [name]

Description: sterile, clear and colourless concentrate for infusion.

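### Section 9.2 orders the drug stopped for any related event that persists to the next day, contradicting the legal notice and section 6.2.1 on who decides treatment

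*Protocol*

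**What the plan says.** Section 9.2, in a paragraph that applies to every recorded related adverse event, states: "Discontinuation of treatment with the study drug is necessary if the related event or its consequences are still present the next day" after the recording of the event. It names no severity grade, seriousness criterion or event type, and gives no rule for restarting. The sentence after it is about further monitoring until the event subsides or stabilises.

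Elsewhere the protocol places treatment decisions outside itself:

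- Legal notice: "This Protocol does not in any way constitute a basis for a decision on any diagnostic or therapeutic methods" for any participant.
- Section 6.2.1: "All patients will use ZOLEDRONIC ACID ACTAVIS in accordance with the decision of the treating physician", and within the conditions of the SPC.
- Section 3.1: "Treatment with this preparation should follow the instructions specified in the Summary of Product Characteristics".
- Section 8.1: "The drugs will be used based on a recommendation by the treating doctor".

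Section 1.2 (study drug) also describes how particular events are managed. For renal function, "serum creatinine should be measured prior to each dose of Zoledronic acid Actavis and treatment should be withheld if renal function has deteriorated", and afterwards "treatment should be resumed at the same dose as that given prior to treatment interruption". For low calcium, phosphate or magnesium it mentions short-term supplementation and does not mention stopping the drug. Section 9.1.3 lists dose reduction and other treatment beside withdrawal among the actions to be reported after an event.

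**The concern.** A non-interventional study records what physicians do and does not direct it. A sentence that makes stopping obligatory directs treatment. It also reaches mild events, which section 9.1.2 defines as leaving the patient's normal functioning unaltered.

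The trigger is the recording of the event, not its onset. Section 7.1.2 also collects related events from before enrolment, and patients enter with at least 30 days of treatment behind them. Read literally, a long-standing, tolerated complaint written down at visit 1 and still present the next day would require the drug to be stopped because the study had recorded it.

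Two things are at stake. The first is patient care: a site that obeyed 9.2 would stop or interrupt treatment to prevent skeletal events on the protocol's order rather than on clinical judgement. The second is the descriptive output. Section 10.4.2 tabulates how many patients discontinued the drug, and section 10.4.3 tabulates those who discontinued for any reason. A stop ordered by 9.2 would be counted there as an ordinary stop in routine care after an adverse event.

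**Working it through.** The protocol gives no figure to reproduce on this point. The check is a comparison of texts, followed by a look at how often the rule could operate.

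**Step 1. Compare 9.2 with each related text.**

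| Place | Content | Relation to 9.2 |
|---|---|---|
| Legal notice | Protocol is no basis for therapeutic decisions | Direct contradiction |
| 6.2.1 | Treating physician decides, within the SPC | Direct contradiction |
| 3.1 | Treatment follows the SPC | Tension only; it does not name who decides |
| 8.1 | Use on the doctor's recommendation, dispensed by a public pharmacy | Tension only; it is mainly about prescribing |
| 9.1.3 | Dose reduction and other treatment listed beside withdrawal | Tension; a universal stop would leave little room for these options |
| 1.2, electrolytes | Short-term supplementation | Tension; no stop is mentioned |
| 1.2, renal | Withhold, then resume at the same dose | Conflict only if 9.2 means a permanent stop |

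**Step 2. Is the stop permanent?** Section 9.2 does not say. Section 9.1.3, in describing certain causality, speaks both of stopping the drug and of starting it again, so in this protocol discontinuation can be temporary. The renal conflict is therefore conditional. The contradictions with the legal notice and 6.2.1 are not, because a compulsory interruption is also a treatment decision taken by the protocol.

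**Step 3. How often could the rule operate?**

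- The schedule in 6.1 has visit 1 and a visit 2 held only if routinely planned. Section 6.2.2 puts visit 2 at least two months after visit 1. Neither section schedules a contact on the day after an event is recorded.
- Dosing for prevention of skeletal events is "4 mg zoledronic acid every 3 to 4 weeks", that is 21 to 28 days. If an event is recorded on a dosing day, the next-day stop falls 21 − 1 = 20 to 28 − 1 = 27 days before the next dose is due. Nothing is withheld until then.
- A stop ordered after a visit 1 record reaches the tables mainly through visit 2, if that takes place. A stop ordered after visit 2 comes after the last scheduled data collection.

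The protocol gives no rate at which related events persist to the next day, so the number of affected patients cannot be calculated.

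**Step 4. Exposure lost per patient, only if the stop is permanent.** Assume a dose at visit 1, no restart, and the regular schedule otherwise kept.

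- Two months (61 days): 61/28 = 2.2 and 61/21 = 2.9, so 2 infusions.
- Four months (122 days): 122/28 = 4.4 and 122/21 = 5.8, so 4 to 5 infusions.

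These counts show what a permanent reading would mean for one patient. They do not estimate the effect of 9.2 as written, because 9.2 does not state permanence.

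**The case against.** The best defence is that the legal notice on the first page already overrides 9.2. Other text points the same way. Section 9.5 treats stopping as contingent even for serious related events, and 9.2 itself asks that ongoing events be checked at each later assessment. The sentence is probably a translation slip for continued follow-up, since its section is about recording and monitoring. The study is descriptive, and section 10.3 disclaims definitive safety conclusions.

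Much of this stands. It limits the size of the problem and makes follow-up the likely intended meaning. It does not remove the contradiction. The protocol states no order of precedence, and investigators sign that they know the responsibilities it places on them. A specific statement that stopping is necessary can be obeyed at one site and ignored at another.

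Three stronger inferences are tempting, and the documents do not support them:

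- *Section 9.2 generally overturns the guidance in 1.2.* The withhold-and-resume text covers renal deterioration only, and a temporary stop is compatible with it.
- *Large numbers would be stopped.* A reader might take the listed frequency of hypophosphataemia, at least 1 in 10, and apply it to 3,500 patients (3,500 × 0.10 = 350). But section 9.1.5 covers laboratory results only where tests were done, and nothing gives the share judged related and still present the next day.
- *The study is in truth interventional, so its basis for omitting consent and ethics review fails.* Sections 4.2 and 13.1 do rest mainly on non-interventional status, and the sentence sits badly with that. But one sentence, probably mistranslated and contradicted elsewhere in the protocol, does not establish that the study was designed to direct treatment.

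**Conclusion.** The point holds in a limited form. As written, 9.2 imposes a treatment change for any related event persisting to the day after it was recorded. That contradicts the legal notice and 6.2.1, and it fits poorly with 3.1, 8.1, 9.1.3 and the electrolyte guidance in 1.2. The conflict with the renal guidance depends on reading the stop as permanent.

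The statistical consequence is narrow: possible protocol-driven stops in the discontinuation tables of 10.4.2 and 10.4.3, in a number that cannot be computed and is probably small. Related adverse events, the main endpoint, are less directly affected, and no test or sample size depends on the sentence. The missed-infusion counts should be used only with the permanent-stop assumption attached. The sentence should still be corrected, because it is an operative instruction that bears on patient care and no other section resolves the conflict.

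**What to change.** Replace the 9.2 sentence with wording such as: *Follow-up is required for as long as the related event or its sequelae persist. Whether treatment is continued, interrupted or stopped is decided by the treating physician in accordance with the SPC.*

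No new form field or reason code is needed. Sections 9.1.3, 9.5 and 12.1 already require the action taken, the distinction between stopping for an adverse event and for lack of effect, and the use of the drug to be recorded. The cost is one amended sentence, with no added patients, visits or tests.

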9.3 Related serious adverse events

9.3.1. The requirements for reporting of adverse events

All serious adverse events related to the use of the study drugs must be reported immediately within 24 hours after obtaining information by the Investigator of the event to the Study Organizer (Europharma). If the first report will be made by telephone, a detailed written CRF should be send.

9.3.2. The mandatory information to be included in the notification of related serious adverse event

The following information are the minimum that should be reported within 24 hours of the occurrence to the Study Organizer representative for all related serious adverse events:

- » number of non-interventional study,
- » centre number,
- » patient number,
- » description of related adverse event,
- » Investigator name and surname, and contact details.

Additional information on the CRF must be provided to the Study Organizer representative as soon as they become available. Upon receipt of the first report Study Organizer will ask the investigator to assess the causal relationship, if such an assessment is not included in the first application.

The Investigator should provide the diagnosis or the name of the disease and not the individual clinical symptoms. The Investigator should also attempt to separate the primary related adverse event (the main adverse event) from the secondary - adverse events that occurred as a complication.

9.4. Deaths

All related adverse events leading to death during the study must be reported as related serious adverse events within 24 hours from the time the investigator was informed about the event.

Death should be reported as follows:

- » Determination of related adverse event: the main cause of death (eg, multi-organ failure, pneumonia, myocardial infarction).
- » **The only exception** is the unknown cause of death (ie, sudden or unexplained death), when the term associated adverse event may be "death" or "sudden death".

9.5. Discontinuation of the treatment with the study drug or withdrawal from the study due to related adverse event as well as related serious adverse event

Discontinuation of the treatment with study drug or discontinuation of patient participation in the study for any reason due to the associated related adverse events should be distinguished from the discontinuation of the study drug or discontinuation of Patient participation in the study for any reason due to lack of therapeutic effect (see section 6).

If the study drug will be discontinued due to a related serious adverse event, this fact must be immediately notified to the representative of the Study Organizer (see section 9.3).

In all cases, the Investigator must provide further appropriate medical care for the patient.

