6. METHODOLOGY

6.1 Schedule of the study

Summary of observations and assessments in the implementation of this study are presented in the following table.

Table1. Schedule of the project

| Procedures for particular visits | Visit 1 | Visit 2* |
|--|---------|----------|
| Demographic data | Х | |
| Data on the primary disease | Х | |
| Qualification of patient to the non-interventional study (inclusion criteria) | Х | |
| History concerning the treatment of the primary disease before the administration of ZOLEDRONIC ACID ACTAVIS formulation | Х | |
| History concerning comorbidities and its treatment | Х | Х |
| History concerning course of treatment and the occurrence of possible adverse events of ZOLE- DRONIC ACID ACTAVIS formulation | Х | Х |
| History concerning tolerance of ZOLEDRONIC ACID ACTAVIS formulation in patient opinion | Х | Х |
| Recording of any changes in the drugs used in comorbidities therapy during treatment with ZOLE- DRONIC ACID ACTAVIS formulation | Х | Х |

* This visit will take place only if it is planned as a part of routine observation of the patient.

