9.1.2 Classification by severity

The related adverse events will be classified as mild, moderate or severe according to the following criteria:

- Mild: symptoms do not alter the normal functioning of the Patient
- Moderate: symptoms cause some degree of dysfunction of the Patient, but are not dangerous, unpleasant or embarrassing to the Patient.
- Severe: symptoms are clearly dangerous for the Patient, cause significant impairment functioning or disability.

9.1.3. Classification according to the a causal relationship between the use of the administered drug and the occurrence of an adverse event

In the Study only adverse events data showing a causal-and-effect relationship with the administration of the study medicinal product will be collected.

Submission of possible and probable (likely time sequence, dose-response relationship) and certain adverse events (good response to discontinuation of the drug or the severity of the adverse events after restarting the drug) related to study medicinal product use will be reported. This report should also include the correct reason and comprehensive information covering the likely time sequence, a good response to treatment withdrawal/reduction of the dose or the severity of the adverse event after restarting the drug/increase the dose; another used pharmacotherapy and procedures – dose decrease, drug withdrawal, optional treatment administered, the effect of used procedure.

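### The protocol does not say how a death whose relationship to the drug cannot be judged is classified or whether it is collected, and it keeps no reliable count of all deaths, so the related-death count cannot be bounded

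*Protocol*

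**What the plan says.** Section 9.1.3 sets the collection filter: "In the Study only adverse events data showing a causal-and-effect relationship with the administration of the study medicinal product will be collected". The classes it names are the ones in its reporting sentence: "Submission of possible and probable (likely time sequence, dose-response relationship) and certain adverse events". It has no class for unrelated events and none for events whose relationship cannot be assessed. Sections 9.3.1 and 9.3.2 likewise speak of serious events related to the drug.

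Section 9.4 opens with its scope: "All related adverse events leading to death during the study must be reported as related serious adverse events within 24 hours". It then says what to write as the event term. The rule is "Determination of related adverse event: the main cause of death (eg, multi-organ failure, pneumonia, myocardial infarction"). The single exception "is the unknown cause of death (ie, sudden or unexplained death), when the term associated adverse event may be" death or sudden death.

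The attribution is the investigator's: "The Investigator must assess the causal relationship between the study drug administration and the occurrence of related adverse events" (9.2). Under 9.3.2 the Study Organizer asks for the assessment if the first report lacks it.

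Other places do not carry the related-only limit in their wording. The synopsis (Endpoints) and 9.6 ask for notification of serious adverse events within 24 hours. Section 9.1.1 lists causing death as a seriousness criterion and asks for any event the investigator considers serious to be reported.

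On follow-up, the footnote to Table 1 (6.1) says of Visit 2: "This visit will take place only if it is planned as a part of routine observation of the patient". Section 7.2 accepts data from either one or two visits.

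**The concern.** Safety is the main aim (2.1), and 10.4 undertakes to assess how often the reported adverse events occur. A drug-related death is the gravest entry those tables can hold. These patients have advanced cancer, and some deaths will reach the clinic with no known cause. For such a death the protocol gives an event term but no rule on relationship, and it filters on relationship at the point of collection.

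Two consequences follow. The number of deaths in the related-event tables depends on how each investigator handles a case that cannot be judged. And because deaths outside that stream are not systematically recorded, a reader of the final report has no all-cause total against which to judge the related count. A statistical analysis plan could not mend this later, because it cannot classify deaths that were never recorded.

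**Working it through.** The plan offers no figure to reproduce: 10.3 fixes about 3,500 patients on practical grounds, and no death rate is given. The check is therefore mainly a comparison of sections.

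**Step 1. One unexplained death, read against each section.** Suppose a patient dies between visits and the clinic learns of it, but not of the cause.

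- An investigator who cannot separate the death from the drug may class it as possible (9.1.3) and enter death or sudden death (9.4). It is counted as related.
- An investigator who sees no causal link shown may take it as outside 9.1.3 and outside the scope of 9.4. It is not collected.
- An investigator who follows 9.1.1 or 9.6 may report it as serious without a causality judgement. The Study Organizer then asks for one (9.3.2). If it still cannot be given, no class fits and no rule says what happens.

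Each can point to a section of the protocol.

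**Step 2. Can the total be recovered elsewhere?**

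- The endpoint (3.2), Table 1 (6.1) and the safety tables (10.4.3) contain no item for all deaths.
- Section 5.4 records the main reason when a patient stops participating, and 10.4.2 tabulates those reasons. Death is not named as a category, and no relationship is attached.
- Section 10.4.2 also counts patients attending later visits. Visit 2 is optional, so those without it mix patients who died with patients who had no routine visit planned.

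A death can surface by these routes, but nothing ensures that it does.

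**Step 3. Illustration of size.** Inputs: N = 3,500 (10.3); u = assumed share of patients dying of unknown cause, which is not in the documents. The number of such deaths is U = N × u. The number counted as related can run from 0 to U. Intervals are exact (Clopper-Pearson) 95%.

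| Assumed u | U = 3,500 × u | None entered as related | All entered as related |
|---|---|---|---|
| 0.1% | 3.5, about 4 | 0 (0%; 0 to 0.11%) | 4 (0.11%; 0.03 to 0.29%) |
| 0.5% | 17.5, about 18 | 0 (0%; 0 to 0.11%) | 18 (0.51%; 0.31 to 0.81%) |
| 1% | 35 | 0 (0%; 0 to 0.11%) | 35 (1.00%; 0.70 to 1.39%) |

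The upper limit with no events is 1 − 0.025^(1/3500) = 0.105%. At 0.5% and 1% the two intervals do not overlap; at 0.1% they do. The two columns are the outer limits of what attribution can do. They do not forecast how investigators will behave.

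**The case against.** A reader might infer that 9.4 turns every unexplained death into a drug-related one and so contradicts 9.1.3. The text does not support that. Section 9.4 is limited from its first sentence to related events that lead to death, and what follows is a rule for naming the event, worded permissively. Read otherwise, its first bullet would also make every death from pneumonia or myocardial infarction drug-related. Unknown cause is also not the same as an unassessable relationship: the possible class in 9.1.3 can hold a death that the investigator cannot separate from the drug, and 9.2 and 9.3.2 require an assessment and a query if it is missing.

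A reader might also infer that a death before Visit 2 triggers no form. That goes too far. Serious-event reporting starts when the investigator is informed, not at a visit. Section 5.4 asks for the reason for leaving, 12.1 for a signed completion page, and 12.2 for a reason where data are missing.

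The heading of 9.6 refers to related events, so its unrestricted sentence may be meant narrowly. A Safety Management plan, mentioned in 9.1.1 and not shown, may say more on the flow of serious events. Section 10.3 calls the study descriptive and disclaims definitive safety conclusions, and related death is not a named endpoint.

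These points rule out a direct contradiction and any claim about actual size. They do not supply a class for a death that cannot be judged, settle whether such a death is collected, or provide a count of all deaths. A descriptive frequency still needs a numerator defined the same way at every site.

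**Conclusion.** The point holds as a gap in the rules. The related-only wording (9.1.3, 9.3) and the unrestricted serious-event wording (synopsis, 9.1.1, 9.6) are not reconciled for deaths. No section covers a death whose relationship cannot be judged. The remaining routes by which a death might be recorded are incidental and name no death category. Followed as written, the related-death count depends on individual attribution, and the data collected will not allow a useful bound on it.

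The size cannot be derived from the documents. The span of 0 to about 18 at an assumed 0.5% of 3,500 is an illustration, and it scales in proportion to the assumed share. Nothing in the protocol supports a comparison with the true rate of fatal reactions: the frequency bands quoted from the product information in 1.2 are for reactions of any outcome. The gap should be closed because it affects what is collected as well as what is tabulated.

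**What to change.** 1. Reconcile the related-only and unrestricted serious-event wording in the synopsis, 9.1.1, 9.1.3, 9.3, 9.4 and 9.6, so that it is clear which deaths are reported.
2. In 9.4 and the Observation Form, record every death of an enrolled patient known to the clinic by the end of observation, regardless of causality: date, cause if known, days since the last infusion, and a causality field that includes 'not assessable'.
3. In 10.4.3, tabulate deaths as related, not assessable and other cause. Give related deaths with and without the not-assessable row, and report the number of patients with unknown vital status.

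The cost is slightly more site work per patient, drawn from existing records, and one extra table. No additional procedure or visit is needed, so the non-interventional design is unchanged. Where Visit 2 does not take place, some patients will remain of unknown vital status; reporting that number shows how far the death count can be relied on.
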